#### ***Physical access***

- a. All Protected Health Information, and all Equipment, Systems and Media must be stored in a secure facility or secure area within ACCF’s facilities which has separate physical controls to limit access, such as locks or physical tokens (“Secured Areas”).
- b. ACCF shall limit access to Secured Areas to those of its employees or agents who have a legitimate business need to access the secure area, and after ACCF has made an administrative determination of the employee’s trustworthiness. Such determination of trustworthiness may include: checking references, checking education and employment history, and searches of public records.
- c. Access to Secured Areas by individuals other than those who have been authorized to access Secured Areas shall only be permitted if there is a legitimate business need, and only if such access is continuously monitored by an employee who has been authorized.
- d. Secured Areas must be monitored 24 hours per day, 7 days per week, either by employees or agents of ACCF by video surveillance, or by intrusion detection systems.

#### ***Electronic access***

- a. Each user who has access to Equipment, Systems and Media (“User”) must have a unique identifier.
- b. Users must be authenticated by one of the following methods: unique token or unique password. ACCF shall prohibit generic user accounts and shall implement inactivity time-outs, where technically feasible, for User devices that access study data.

#### ***Wireless Devices***

Encryption of wireless network data transmission and authentication of wireless devices containing study data ACCF’s network is required.

#### ***Transmission of Protected Health Information***

Protected Health Information may only be transmitted off ACCF’s premises to approved parties, Electronic Protected Health Information may only be transmitted via encrypted and authenticated channels, such as VPN, encrypted FTP, SSL or HTTPS.

#### ***External Access***

### ***Internet***

If any Equipment, Systems or Media have Internet connectivity, users must be advised that their unique identifier and authentication tool (e.g. password) must not be shared with others. Where password authentication is employed to authenticate Users, ACCF access and communication to or from the Internet must occur through an actively managed Internet firewall service.

### ***Remote access***

If any employees or agents of ACCF have remote access to Protected Health Information, or to Equipment, Systems and Media, from offsite locations, ACCF shall adopt systems and procedures to secure such connections and transmissions. At a minimum, ACCF must ensure the following: 1) dial-up access will occur through a technical security service such as Remote Authentication Dial-In User Service (RADIUS); 2) access via the Internet will be controlled via secure technologies to include authentication and encryption. Acceptable technologies include firewalls and virtual private network services; and 3) ACCF shall require users who access Protected Health Information via personally owned devices and remote access services to take responsibility for the integrity and security of their systems and employ anti-virus software and apply operating system service packs as they are released. Protected Health Information may not be stored on personally owned devices.

### ***Software Controls***

#### ***Virus Protection***

ACCF shall employ virus protection on systems or networks that store, process, access or transmit Protected Health Information, and such protection systems must include real-time or periodic scans.

#### ***Service Packs and Security Patches***

ACCF shall apply operating system service packs and security patches to systems or networks that store, process, access or transmit Protected Health Information as soon as practicable after they are released.

#### ***Audit***

ACCF shall implement technical features or controls to record security-relevant activity. ACCF periodically reviews activity logs, investigates and resolves incidents where unauthorized access and attempts are identified. ACCF shall maintain audit logs.

#### ***Violations***

ACCF shall have a process in place for employees to report instances of violations of privacy and security policies and procedures to the appropriate ACCF personnel.

#### ***Transportation and Transmission of Protected Health Information***

Protected Health Information, and Equipment, Systems and Media may not be transported off of ACCF's premises unless such Protected Health Information is encrypted.

#### ***Disposal of files or media which contain Protected Health Information.***

If ACCF is required to destroy files or media containing Protected Health Information pursuant to the Business Associate Agreement, such destruction shall be performed in the following manner:

*Magnetic Media*

Magnetic Media such as tapes, diskettes, hard drives, must be purged of all information such that the data is no longer reasonably retrievable from the media. Degaussing is an acceptable method of purging information from magnetic media.

*Non-Magnetic Media*

Non-magnetic media such as hard copies, CDs or DVDs must be physically destroyed such that the data is no longer reasonably retrievable from the media. Acceptable methods of physical destruction include shredding.

TRANSFORM participating collaborators shall employ comparable safeguards that store, process, access or transmit Protected Health Information with real-time protection. No printed materials will be generated as part of this study.

## **Informed Consent**

---

In all arms, clinician choice will not be restricted and care recommendations will not be mandated. These quality improvement initiatives are all clinician-facing to promote best practice / guideline recommended care and supported by a linked patient application, to support data collection and clinician engagement. All study arms can be considered standard of care, and no investigation intervention or therapy is being provided. All PCPs and cardiologists will receive a correspondence prior to the start of the study describing the initiative. Any clinician who does not wish to receive the quality improvement communication will be allowed to opt-out such that all patients under their direct care will not be eligible for the study. At any time during the study, clinicians may decide to similarly opt-out.

Eligible patients will be enrolled via paper consent or electronically utilizing software services provided by Biofourmis.

Consent materials will be provided with sufficient time for the patient to consider their participation in the study. All consent materials will be in the patients' native language and will describe the quality improvement nature of the study and that data collection of therapies will be tracked.

If the patient agrees to participation in the study via paper, the informed consent and signature will be stored at the study site and/or the Biofourmis platform.

If the patient agrees to participation in the study electronically, their informed consent will be recorded through e-consent processes with signature stored at Biofourmis with a copy to the study site. At any time, patients may withdraw consent. In such a circumstance, patients will be analyzed per intent to treat. Only those patients capable of giving informed consent will be enrolled in the study.

There are no costs or compensation to the patient for participation in the TRANSFORM study.

## APPENDIX

### PDF/Printable Materials

#### Heart Failure

##### Action Plans

[Your Action Plan for Heart Failure With Preserved Ejection Fraction \(HFpEF\)](#)

[Your Action Plan for Heart Failure With Reduced Ejection Fraction \(HFrEF\)](#)

##### Worksheets

[Heart Failure: Making the Most of Your Follow-Up Visits](#)

[Your Heart Failure Daily Tracker](#)

[Your Heart Failure Checklist](#)

##### Quick Tips

[Quick Tips Sheet: Daily Weight Check](#)

[Quick Tips Sheet: Minding Your Emotional Health](#)

[Quick Tips: Exercise and Your Heart](#)

[Quick Tips: Heart Failure Medications](#)

[Quick Tips: Limiting Salt](#)

[Quick Tips: Heart Failure Signs and Symptoms](#)

[Quick Tips: Triggers and What To Do](#)

##### More Resources

[Heart Failure, The Basics](#)

[Heart Failure: Questions to Ask](#)

[Heart Failure: Frequently Asked Questions](#)

[Heart Failure: What Your Treatment Plan Might Include](#)

[Heart Failure: Caregivers](#)

#### Action Plan

- [Your Action Plan for Managing Atrial Fibrillation](#)

#### Worksheets

- [AFib Medication List](#)
- [10 Steps You Can Take to Manage Atrial Fibrillation](#)
- [Keeping Track of Symptoms and How AFib Affects Your Life](#)
- [AFib Symptom Diary](#)

#### Action Plan

- [Your Action Plan for Managing Diabetes and Protecting Your Heart](#)

#### Worksheets

- [Diabetes and Heart Disease: What You Need to Know:](#)
- [10 Steps to Lower Your Chance of Diabetes-Related Heart Problems:](#)
- [My Medication List:](#)

## Patient Survey Questions

### CardioSmart E-Diary

Source: [Cardiosmart.org](http://Cardiosmart.org)

1. Here is how I would describe I feel today
  - a) A good day with heart failure
  - b) A bad day with heart failure
  - c) My worst day with heart failure
2. On a scale from 0 to 10, my stress or anxiety level is (0-10)
3. On a scale from 0 to 10, how sad or depressed have I been feeling? (0-10)
4. Generally, how am I coping with my [heart disease] diagnosis?
  - a) Very poorly
  - b) Poorly
  - c) Ok
  - d) Pretty well
  - e) Very well, all things considered
5. Overall, describe the stage you are at in living with [heart disease]
  - a) Acceptance
  - b) Denial
  - c) Anger
  - d) Depressed

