## Rationale and Background

---

TRANSFORM is a Quality Improvement initiative conducted in parallel to the current TRANSFORM CVRiD study and aligned with its goals of using a real-world population study to enable the American College of Cardiology Foundation (“ACCF”) to better identify impactful ways to improve guideline directed medical therapy for patients. TRANSFORM is focused on improving GDMT use in underserved patients and patients with a history of health care disparities who have one or more of the following: heart failure, atrial fibrillation, and ASCVD/Type 2 diabetes.

There is a significant disconnect between increasing availability of effective and safe therapeutics that significantly reduce CV event risk in patients with Heart Failure, T2D and ASCVD, and Atrial Fibrillation—and clear guideline recommendations endorsing these therapies—but very low adoption in clinical practice with the majority of eligible patients that are most likely to benefit from these therapies not receiving them. A high proportion of patients have more than one of these conditions further reducing the chances of receiving optimal guideline directed medical therapy and avoiding the CV events they are designed to prevent.

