**Population:**

**750 total with comorbidity overlap (250 HFrEF, 250 HFpEF, 500 AF, 250 T2D/ASVD)**

*Inclusion criteria:*

1. Age  $\geq 18$  years
2. Personal access to a computer and/or smartphone for app download
3. Heart Failure (reduced and preserved ejection fraction) AND/OR
4. Atrial Fibrillation with CHA2DS2-VASc score greater than or equal to 2 in men and greater than or equal to 3 in women AND/OR
5. T2D and ASCVD, defined as follows:
  - a. Known CAD, prior ACS, or coronary artery revascularization
  - b. Prior TIA/stroke or known carotid or intracerebral atherosclerosis
  - c. Prior PAD including requiring revascularization

*Exclusion criteria:*

- All patients
  - Current or anticipated participation in an interventional clinical trial of a drug/device
  - Currently receiving comfort care or enrolled in hospice
  - Life expectancy <1 year
  - Pregnancy or active breastfeeding
  - Current or anticipated participation in an interventional clinical trial (other than TRANSFORM GDMT)
  - Patients without a clinical encounter within three years of study start date
- Heart Failure patients:
  - History of or plan for heart transplantation or left ventricular assist device
  - Palliative chronic inotropic therapy
  - NYHA Class 4 heart failure
- Atrial Fibrillation patients:
  - Current prescription for OAC
  - Reversible cause of atrial fibrillation, such as post-cardiothoracic surgery or thyrotoxicosis
  - History of ischemic stroke in prior 7 days
  - Transient ischemic attack in prior 3 days
  - Platelet count <70,000/ml
  - Hemoglobin concentration <8g/dl
  - History of or condition associated with increased bleeding risk, such as hemophilia
  - History of mechanical valve replacement
  - Major surgical procedure or trauma within 14 days
  - Clinically significant gastrointestinal bleeding within 8 weeks

- History of intracranial, intraocular, spinal, or atraumatic intra-articular bleeding
- T2D/ASCVD patients with or without HF or AF:
  - Current prescription for SGLT2i and GLP-1RA
  - Current or planned hemodialysis
  - Decompensated end stage liver disease
  - Type 1 diabetes
  - Prior diabetic ketoacidosis
  - Gestational diabetes
  - History of pancreatitis or pancreatic cancer

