#### **Secondary Objective**

##### TRANSFORM:

1. Difference in patient reported outcome scores specifically;
  - a) Difference in patient reported outcomes on Morisky Medication Adherence Scale (MMAS-4) from baseline, 3 and at 9 months
  - b) Difference in patient reported outcomes on Patient Activation Measure® (PAM) from baseline, 3 and at 9 months
  - c) Difference in patient-reported outcome/KCCQ-12 scores from baseline to 9 months (applicable to HFrEF and HFpEF study cohorts only)

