#### **Implementation Efficacy Measures:**

- We will assess engagement with the technology and referral completion rates by patients
- Short questionnaires (PAM, MMAS-4, KCCQ-12, CardioSmart E-Diary) will be completed at baseline by patient participants to determine any patient factors that may modify the responses to each of the intervention arms (centered around baseline perception of care optimization, perceived cardiovascular risk, willingness to take new therapy, clinician trust / therapeutic relationship). See appendix.

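### CardioSmart E-Diary item 1 offers only heart-failure answers, although the protocol does not limit the diary to patients with heart failure

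*Protocol*

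**What the plan says.** The protocol appendix (Patient Survey Questions, CardioSmart E-Diary) sets out five items. Item 1 asks how the patient feels today and offers three answers. The first is "A good day with heart failure"; the second and third describe a bad day and the worst day, again with heart failure. No further option is printed. Items 2 and 3 are 0 to 10 scales that name no disease. Item 4 reads "Generally, how am I coping with my [heart disease] diagnosis", and item 5 carries the same bracketed term.

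Implementation Efficacy Measures states who completes the diary: "Short questionnaires (PAM, MMAS-4, KCCQ-12, CardioSmart E-Diary) will be completed at baseline by patient participants". It also states why: the questionnaires "will be completed at baseline by patient participants to determine any patient factors that may modify the responses" to each arm. Mixed Methods Evaluation and the Qualitative Surveys paragraph also speak of patient participants without a disease limit.

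Heart failure is not required for entry. Rationale and Background describes patients with "one or more of the following: heart failure, atrial fibrillation, and ASCVD/Type 2 diabetes", and the inclusion criteria join the conditions in the same way: "Heart Failure (reduced and preserved ejection fraction) AND/OR". The planned numbers are "750 total with comorbidity overlap (250 HFrEF, 250 HFpEF, 500 AF, 250 T2D/ASVD".

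Where the protocol wants a heart-failure limit on an instrument, it writes one. Under Secondary Objective, KCCQ-12 is "applicable to HFrEF and HFpEF study cohorts only".

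**The concern.** A patient with only atrial fibrillation, or only T2D/ASCVD, cannot truthfully choose any printed answer to item 1. Such a patient either leaves it blank or describes a disease that he or she does not have. The bracketed term in items 4 and 5 suggests that the diary was meant to serve more than one diagnosis and that item 1 was not adapted.

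The stake is the stated exploratory use. If item 1 is blank mainly in patients without heart failure, then answered versus missing follows disease cohort. If the app forces a choice, the answers of those patients carry no meaning. The cohorts have different outcome definitions and, in Power Estimates, very different baseline rates: 15% for SGLT2i or GLP-1RA use, 2% for optimal HFrEF therapy and 60-65% for anticoagulation in atrial fibrillation. A modifier effect found on a pooled item 1 could therefore partly be a difference between cohorts. Randomisation does not remove this, because the entanglement is between the modifier and the cohort, not between the arms.

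An analysis plan can decide how to treat missing or inapplicable answers. It cannot recover a valid answer that the form never offered.

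**Working it through.** **The wording, side by side**

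| Diary item | Disease named | Can a patient without heart failure answer? |
|---|---|---|
| 1 (feeling today) | Heart failure in all three answers | No |
| 2, 3 (stress, mood) | None | Yes |
| 4, 5 (coping, stage) | Generic bracketed term | Yes, if that term is kept |

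**How many patients**

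The protocol gives no figure for patients without heart failure, so there is none to reproduce. It follows from the Population targets: 750 in total, 250 HFrEF, 250 HFpEF, 500 atrial fibrillation, 250 T2D/ASCVD.

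1. Memberships: 250 + 250 + 500 + 250 = 1,250 in 750 patients, so many patients belong to more than one cohort.
2. Patients with heart failure, taking HFrEF and HFpEF as mutually exclusive: 250 + 250 = 500.
3. Patients without heart failure: 750 - 500 = 250; 250 / 750 = 33.3%.
4. Per arm at 1:1:1: 250 / 3 = about 83.

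**Sensitivity (assumed departures, total fixed at 750)**

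| Assumption | With HF | Without HF | Share |
|---|---|---|---|
| HF accrual 20% over target | 600 | 150 | 20.0% |
| HF accrual 10% over target | 550 | 200 | 26.7% |
| Targets met exactly, no overlap | 500 | 250 | 33.3% |
| 25 patients counted in both HF cohorts | 475 | 275 | 36.7% |
| 50 patients counted in both HF cohorts | 450 | 300 | 40.0% |

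These departures are illustrations and do not bound the share. If heart failure accrual ran 50% over target, all 750 patients would have heart failure and the share would be zero.

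**What item 1 feeds**

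The Primary Objective concerns prescription of drug classes. The Secondary Objective names MMAS-4, PAM and KCCQ-12 as patient-reported outcomes, not the diary. The Intervention table lists patient perception as a secondary outcome without naming an instrument, and nothing ties it to item 1. The sample size rests on prescription rates. The only stated use of the diary is as a baseline modifier.

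**The case against.** The strongest case on the other side has five parts.

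- **The diary may not be meant for everyone.** The sentence that lists the questionnaires also lists KCCQ-12, which is limited to heart failure elsewhere, so the list alone does not prove that each instrument goes to each patient. This stands: that all participants receive the diary is a reading of unrestricted wording, not a stated fact. But no section limits the diary, and four of its five items suit any cohort. If it was meant for heart failure only, the protocol still needs to say so.
- **The appendix may show a template.** The unfilled brackets and the cited web source point that way, and the app might hide or reword item 1. That is possible, but the protocol describes no such handling.
- **The confounding is conditional.** This stands. It arises only if item 1 is pooled across cohorts. Within the heart failure cohorts the item is valid and cannot stand in for having heart failure. The protocol also centres the modifier work on perceptions, risk, willingness and trust, none of which item 1 measures, and it describes no model that uses the item.
- **The count is soft.** This stands too. Randomization Scheme keeps enrolment open until targets are met, so the cohort figures work more as minimums than as final counts.
- **Arms stay comparable.** Allocation is by patient, so inapplicable answers should fall similarly in each arm. This is accepted.

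A reader might also infer that KCCQ-12 has the same fault, because Implementation Efficacy Measures lists it without a disease limit. The documents do not support that: Secondary Objective already confines it to the heart failure cohorts, and the two sections do not conflict.

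**Conclusion.** The point holds as a minor defect of the instrument. As printed, item 1 has no valid answer for a patient without heart failure, and the protocol both enrols such patients and puts no limit on who completes the diary. About a third of the planned sample is affected if cohort targets are met exactly and the two heart failure cohorts do not overlap.

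A reader might infer that item 1 is a proxy for heart failure, or that the modifier analysis is already confounded. The documents do not go that far: they name no analysis of item 1, and the problem would need pooling across cohorts. The loss is one baseline item in an exploratory exercise. The defined endpoints, the sample size and the comparisons between arms are untouched.

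**What to change.** Any one of three changes is enough:

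- Reword the three item 1 answers with the same generic term as items 4 and 5.
- Keep the answers and add a not-applicable option.
- State that item 1, and its use as a modifier, is confined to the heart failure cohorts.

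If the first is chosen, use one fixed term rather than each patient's own condition. With 1,250 cohort memberships planned in 750 patients, the own condition is undefined for many of them. The generic term also fits less well for a patient who qualifies through T2D with prior stroke or peripheral artery disease alone; the second and third options avoid that difficulty.

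The cost is a wording or display change in the app questionnaire and the matching line in the appendix or in Implementation Efficacy Measures. It should be made before baseline collection, because answers already given cannot be repaired. Where some have been collected, item 1 should be analysed only within the heart failure cohorts.

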### Morisky Medication Adherence Scale (MMAS-4) (Yes/No)

Source: [1569058438 \(768x1024\) \(scribdassets.com\)](https://www.scribd.com/document/1569058438/768x1024)

1. Do you ever forget to take your medicine?
2. Are you careless at times about taking your medicine?
3. Sometimes, if you feel worse when you take your medicine, do you stop taking it?
4. When you feel better, do you sometimes stop taking your medicine?

Page Break

### Patient Activation Measure (PAM)

Source: <https://www.insigniahealth.com/research/research-licenses>

(Disagree Strongly, Disagree, Agree, Agree Strongly)

1. When all is said and done, I am the person who is responsible for taking care of my health
2. Taking an active role in my own health care is the most important thing that affects my health
3. I am confident I can help prevent or reduce problems associated with my health
4. I know what each of my prescribed medications do
5. I am confident that I can tell whether I need to go to the doctor or whether I can take care of a health problem myself
6. I am confident that I can tell a doctor concerns I have even when he or she does not ask
7. I am confident that I can follow through on medical treatments I may need to do at home
8. I understand my health problems and what causes them
9. I know what treatments are available for my health problems
10. I have been able to maintain (keep up with) lifestyle changes, like eating right or exercising
11. I know how to prevent problems with my health

12. I am confident I can figure out solutions when new problems arise with my health
13. I am confident that I can maintain lifestyle changes, like eating right and exercising even during times of stress

